14.4 Clinical Outcomes that may be Exempt from Adverse Event Recording and Reporting

In this study of critically ill patients at high risk for death and other adverse outcomes due to their underlying critical illness, clinical outcomes, including death and organ dysfunction, will be systematically collected and analyzed for all patients. The primary, secondary, safety, and exploratory outcomes will be recorded and reported as clinical outcomes and not as adverse events unless treating clinicians or site investigators believe the event is Definitely Related or Probably or Possibly Related to the study intervention or study procedures. This approach – considering death and organ dysfunction as clinical outcomes rather than adverse events and systematically collecting these clinical outcomes for analysis – is common in ICU trials. This approach ensures comprehensive data on death and organ dysfunction for all patients, rather than relying on sporadic adverse event reporting to identify these important events. The following events are examples of study-specific clinical outcomes that would not be recorded and reported as adverse events unless treating clinicians or site investigators believe the event was Definitely Related or Probably or Possibly Related to the study intervention or study procedures:

- Death (all deaths occurring prior to hospital discharge or 28 days will be recorded);
- Organ dysfunction
 - Pulmonary – hypoxemia, aspiration, acute hypoxic respiratory failure, pneumothorax
 - Cardiac – hypotension, shock, vasopressor receipt, cardiac arrest;
- Duration of mechanical ventilation;
- Duration of ICU admission;
- Duration of hospitalization

Note: A study-specific clinical outcome may also qualify as an adverse event meeting criteria for recording and reporting. For example, a pneumothorax that the investigator considers Definitely Related to preoxygenation with non-invasive positive pressure ventilation would be both recorded as a study-specific clinical outcome and recorded and reported as a Serious and Definitely Related adverse event.

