- body fluids anticipated to obscure laryngeal view
- operator's level of training and specialty
- operator's prior intubation experience

Peri-procedural:

Enrollment to induction

- SpO₂ and FiO₂ at enrollment
- oxygen saturation from enrollment to induction
- approach to preoxygenation
- duration of preoxygenation

Induction to first laryngoscopy attempt

- time of sedative administration (induction)
- sedative agent and dose
- neuromuscular blocking agent and dose
- administration of an intravenous fluid bolus prior to induction
- administration of a vasopressor prior to induction
- SpO₂ at induction
- systolic blood pressure at induction
- approach to oxygen administration and ventilation between induction and laryngoscopy

First laryngoscopy attempt to successful intubation

- time of start of first laryngoscopy attempt
- laryngoscope model, blade size, blade shape on first attempt
- use of video screen (if applicable) on first laryngoscopy attempt
- best Cormack-Lehane grade of glottic view on the first laryngoscopy attempt
- presences of body fluids obstructing laryngeal view
- presence of upper airway obstruction or edema
- receipt of chest compressions at time of first laryngoscopy attempt
- number of intubation attempts
 - number of times laryngoscope entered mouth
 - number of times bougie entered mouth (if applicable)
 - number of times endotracheal tube entered mouth
- reason for failure of first intubation attempt (if applicable)
- device(s) used on subsequent intubation attempts (if applicable)
- necessity of an additional operator
- esophageal intubation
- injury to the teeth
- operator-reported aspiration between induction and intubation
- time of successful tracheal intubation
- endotracheal tube size
- lowest SpO₂ from induction until 2 minutes after intubation
- lowest systolic blood pressure from induction until 2 minutes after intubation
- new or increased vasopressor use from induction until 2 minutes after intubation
- cardiac arrest from induction until 2 minutes after intubation not resulting in death within 1 hour of induction

- cardiac arrest from induction until 2 minutes after intubation resulting in death within 1 hour of induction

In-hospital:

24 hours after enrollment

- new pneumothorax detected in the first 24 hours after enrollment
- vasopressor receipt at 24 hours after enrollment
- SpO₂ at 24 hours after enrollment
- FiO₂ at 24 hours after enrollment
- PEEP at 24 hours after enrollment

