14.2 Monitoring for Adverse Events

The time interval during which patients will be monitored for the occurrence of adverse events

begins at randomization and ends at the first of hospital discharge or 28 days. Adverse events occurring before randomization or after hospital discharge or 28 days will not be collected. The lead investigator at each enrolling site will have primary responsibility overseeing the monitoring, assessment, and reporting of adverse events. Site study personnel will evaluate for the occurrence of adverse events by manual review of the electronic health record and by communication with treating clinicians. Site study personnel will evaluate for the occurrence of adverse events by manual review of the electronic health record at two time points. The first will occur approximately 24 hours after randomization at the time of initial data collection. The second will occur at the first of hospital discharge or 28 days after enrollment at the time of final data collection. Study personnel at each site will also communicate regularly with the treating clinicians who perform tracheal intubation in the study environments between enrollment and 28 days after enrollment to solicit information about any potential adverse events. If study personnel at a site identify a potential adverse event, the lead investigator at the site will be immediately notified. The lead investigator at the site will assess the seriousness, unexpectedness, and relatedness of the potential adverse event. With assistance as needed from the coordinating center and the trial primary investigator, the lead investigator at the site will determine whether the event qualifies for recording and reporting.

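### Section 14.4 exempts listed organ-dysfunction events with no time limit, so a non-fatal late event of Uncertain Relationship that 14.3 would record enters neither the adverse event nor the outcome data

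*Combined protocol and SAP*

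**What the plan says.** Protocol v1.1, section 14.4, treats certain events as clinical outcomes and not as adverse events. The organ-dysfunction examples are "Pulmonary – hypoxemia, aspiration, acute hypoxic respiratory failure, pneumothorax" and "Cardiac – hypotension, shock, vasopressor receipt, cardiac arrest". Death and the durations of ventilation, ICU stay and hospitalization are also listed. No time limit is attached to any organ-dysfunction event. The exemption applies "unless treating clinicians or site investigators believe the event was Definitely Related or Probably or Possibly Related to the study intervention" or study procedures. The justification is that outcome collection replaces adverse event reporting: "This approach ensures comprehensive data on death and organ dysfunction for all patients, rather than relying on sporadic adverse event reporting".

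Section 14.3 sets the general rule. It records events that are serious or unexpected and whose relationship is definite, probable or possible, or uncertain, and it records nothing else.

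Section 14.2 sets the monitoring period, which "begins at randomization and ends at the first of hospital discharge or 28 days".

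Section 9 sets the collection windows. Two examples are "cardiac arrest from induction until 2 minutes after intubation not resulting in death within 1 hour of induction" and "new pneumothorax detected in the first 24 hours after enrollment".

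**The concern.** The exemption is an exchange: an event may leave the adverse event forms because it is counted systematically elsewhere. That works only if the outcome item covers the same event over the same period. Here the exemption runs over the whole monitoring period, while most of the matching items close within minutes or a day and some do not exist.

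Section 14.4 also names fewer relatedness classes than 14.3. Uncertain Relationship is reportable in one section and missing from the exception in the other.

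At stake is the ability to compare the arms on harms just after the procedure. Relatedness is judged by people who know the assignment, so it cannot stand in for systematic counting. There is also a procedural cost. Section 14.3 gives the final relatedness determination to the coordinating center and the principal investigator, but an event exempted at the site under 14.4 produces no adverse event record for them to review.

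**Working it through.** The plan gives no figure to reproduce here, so the check sets the sections side by side.

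**Step 1. Match each exempt event to its listed item (protocol v1.1, sections 8.1 to 8.4 and 9).**

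| Exempt in 14.4 | Listed item | Coverage |
|---|---|---|
| Cardiac arrest | Yes | Induction to 2 min after intubation |
| Hypotension | Lowest systolic pressure | Same window, plus one reading at 24 h |
| Vasopressor receipt | New or increased use | Same window, plus status at 24 h |
| Hypoxemia | Lowest saturation | Same window, plus one reading at 24 h |
| Aspiration | Operator report | Induction to intubation |
| Pneumothorax | Yes | 24 h |
| Shock | None of its own | Indirect: 24 h vasopressor and pressure |
| Acute hypoxic respiratory failure | None of its own | Indirect: 24 h SpO2, FiO2, PEEP |
| Duration of hospitalization | None of its own | None listed |
| Death | Yes | Discharge or 28 days |
| Ventilator and ICU time | Ventilator-free and ICU-free days | 28 days |

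Only the last two rows match the monitoring period in 14.2.

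**Step 2. Can the exemption be read as limited to defined outcomes inside their windows?** No. Shock, acute hypoxic respiratory failure and duration of hospitalization are on the exempt list but are not outcomes in section 8.

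**Step 3. Pass one event through both rules.** Take a listed, non-fatal event that is serious or unexpected and falls outside its outcome window, or has no outcome.

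| Relatedness class (14.1) | Recorded under 14.3 alone | Recorded after 14.4 | Lost because of 14.4 |
|---|---|---|---|
| Definitely Related | Yes | Yes | No |
| Probably or Possibly Related | Yes | Yes | No |
| Uncertain Relationship | Yes | No | **Yes** |
| Probably Not Related | No | No | No |
| Definitely Not Related | No | No | No |

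Section 14.4 changes the result in 1 of 5 classes. An event of Uncertain Relationship inside its window is also exempt, but it is counted as an outcome, so nothing is lost there.

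**Step 4. Length of the uncovered period.** The longest organ-dysfunction window is 24 h. Against the 28-day maximum it covers 1/28 = 3.6%, leaving 27/28 = 96.4%. For cardiac arrest, Figure 1 of the published SAP gives nominal phases of 45 to 90 s from induction to laryngoscopy and 45 to 90 s from laryngoscopy to intubation. Adding 120 s gives 2 × (45 to 90) + 120 = 210 to 300 s, or 3.5 to 5 minutes.

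**Step 5. Number of events.** This cannot be computed. The documents give neither a rate for arrests or pneumothoraces after these windows nor the share that sites would class as uncertain.

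**The case against.** A reader might infer that 14.4 removes these events outright, so that every late event enters neither dataset. The documents do not support that. Events believed at least possibly related stay in adverse event recording; 14.4 gives a related pneumothorax as its example. Events judged unrelated are dropped by 14.3, with or without 14.4. Fatal events count in 28-day in-hospital mortality. Ventilator-free days, ICU-free days and the 24-hour readings catch part of late organ failure.

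A reader might also try to count lost arrests from the 1-in-25 figure in section 10.1. That figure states no window, and nothing says what fraction falls after 2 minutes. Nor does section 10.2 name all of these harms as possibly differing between arms. It names hypoxemia, hypotension, cardiac arrest and aspiration, with a general phrase for others, but not pneumothorax, shock or respiratory failure.

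Four further objections carry some weight:

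- **The variable list may be incomplete.** The SAP refers to a supplementary variable table that is not in the documents. Section 9 is not exhaustive, since it omits new infiltrate, a safety outcome in 8.3. The absence of a listed item is therefore not proof that nothing is collected.
- **Uncertain Relationship is a residual class.** Under 14.1, an arrest minutes after intubation could be called possibly related on temporal sequence alone, and would then be recorded.
- **Short windows suit a one-time intervention** that ends by laryngoscopy, and the SAP manuscript lets the DSMB request more data.
- **The closing note in 14.4** says a clinical outcome may also qualify as a recordable adverse event, which could be taken to leave 14.3 intact.

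These objections limit the size of the point but do not remove it. The exception in 14.4 is stated twice and omits Uncertain Relationship both times, and the note's only example is a definitely related event. Short windows are defensible as outcome definitions, but not as grounds for an exemption without a time limit. The DSMB's power to ask for data does not make the data systematically collected.

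**Conclusion.** The point holds in a narrow form. Two things are wrong.

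1. **A rule conflict.** Sections 14.3 and 14.4 disagree on events of Uncertain Relationship. A serious or unexpected, non-fatal listed event of that class, outside its outcome window or without an outcome, is recordable under one section and removed by the other.
2. **An unsupported assurance.** The listed items are not comprehensive for organ dysfunction. Beyond 24 hours they reach only mortality, ventilator-free days and ICU-free days.

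The conclusion assumes that 14.4 overrides 14.3 for listed events, as its wording indicates, and that the missing supplementary table adds no items that close the gap. The primary and secondary analyses are unaffected. The change is worth making because it concerns safety data and costs little.

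**What to change.** - **Section 14.4, exemption.** Limit it to events that meet both the definition and the time window of a listed outcome. Send every other listed event, including those of Uncertain Relationship, to 14.3, so that the two sections agree. This recovers the uncertain class only; events judged unrelated stay outside adverse event recording under 14.3.
- **24-hour record review (14.2).** Add one item, cardiac arrest from randomization to 24 hours (yes/no), and tabulate it by arm for the DSMB. Early post-procedure arrests can then be compared whatever the unblinded relatedness call.
- **Completeness sentence in 14.4.** Restrict it to what is collected, giving the windows. If the other two changes are not adopted, this one is still needed.

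The cost is a sentence or two in 14.4, one extra item on a chart review that already takes place, and somewhat more adverse event forms in a very sick population.

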14.5 Unanticipated Problems involving Risks to Subjects or Others

Investigators must also report Unanticipated Problems Involving Risks to Subjects or Others (“Unanticipated Problems”), regardless of severity, associated with study procedures **within 24 hours** of the site investigator becoming aware of the Unanticipated Problem. An Unanticipated Problem is defined as any incident, experience, or outcome that meets all of the following criteria:

- Unexpected (in terms of nature, severity, or frequency) given (a) the research procedures that are described in the protocol-related documents, such as the IRB-approved research protocol; and (b) the characteristics of the subject population being studied; AND
- Definitely Related or Probably or Possibly Related to participation in the research (as defined above in the section on characteristics of adverse events); AND
- Suggests that the research places subjects or others at a greater risk of harm (including physical, psychological, economic, or social harm) than was previously known or recognized.

If any study personnel at a site become aware of an event that may represent an Unanticipated problem, they will immediately contact the lead investigator for the site. The lead investigator for the site will assess whether the event represents an Unanticipated Problem by applying the criteria described above. If the lead investigator at a site determines that the event represents an Unanticipated Problem, the lead investigator at the site will record the Unanticipated Problem in the Unanticipated Problem electronic case report form in the trial database. The lead investigator at the site will then communicate that an Unanticipated Problem has occurred to the coordinating center and the principal investigator **within 24 hours** of the lead investigator at the site becoming aware of the Unanticipated Problem. The coordinating center and principal investigator will coordinate with the lead investigator at the site to obtain information about the Unanticipated Problem. The coordinating center will report the Unanticipated Problem to the DSMB, IRB, and sponsor within 15 days of becoming aware of the Unanticipated Problem.

15. Data and Safety Monitoring Board (DSMB)

The principal role of the DSMB is to assure the safety of patients in the trial. They will regularly monitor data from this trial, review and assess the performance of its operations, and make recommendations to the steering committee and sponsor with respect to:

- Participant safety and risk/benefit ratio of study procedures and interventions
- Initial approval of the protocol and subsequent amendments (with specific attention to study population, intervention, and study procedures)
- Adherence to the protocol requirements
- Completeness, quality, and planned analysis of data
- Ancillary study burden on participants and main study
- Possible early termination of the trial because of new external information, early attainment of study objectives, safety concerns, or inadequate performance

The DSMB will consist of members with expertise in bioethics, emergency medicine, pulmonary and critical care medicine, anesthesia, biostatistics, and clinical trials. Appointment of all members is contingent upon the absence of any conflicts of interest. All the members of the DSMB are voting members. The coordinating center, principal investigators, and unblinded study biostatistician will be responsible for the preparation of all DSMB and adverse event

reports. The DSMB will develop a charter and review the protocol and patient notification forms during its first meeting. Subsequent DSMB meetings will be scheduled in accordance with the DSMB Charter. The DSMB will have the ability to recommend that the trial end, be modified, or continued unchanged.

References

3. Leibowitz AB. Tracheal intubation in the intensive care unit: extremely hazardous even in the best of hands. *Crit Care Med* 2006; 34: 2497-2498.

Study Design and Methods: The PRagmatic trial Examining OXygenation prior to Intubation (PREOXI) is a prospective, multicenter, non-blinded randomized comparative effectiveness trial being conducted in 7 emergency departments and 17 intensive care units across the United States. The trial compares preoxygenation with noninvasive ventilation versus oxygen mask among 1300 critically ill adults undergoing emergency tracheal intubation. Eligible patients are randomized in a 1:1 ratio to receive either noninvasive ventilation or an oxygen mask prior to induction. The primary outcome is the incidence of hypoxemia, defined as a peripheral oxygen saturation <85% between induction and 2 minutes after intubation. The secondary outcome is the lowest oxygen saturation between induction and 2 minutes after intubation. Enrollment began on 10 March 2022 and is expected to conclude in 2023.

Interpretation: The PREOXI trial will provide important data on the effectiveness of noninvasive ventilation and oxygen mask preoxygenation for the prevention of hypoxemia during emergency tracheal intubation. Specifying the protocol and statistical

analysis plan prior to the conclusion of enrollment increases the rigor, reproducibility, and interpretability of the trial.

Clinical trial registration number: NCT05267652

INTRODUCTION

Life-threatening hypoxemia occurs in 10-20% of emergency tracheal intubations in the Emergency Department (ED) and Intensive Care Unit (ICU).^{1,2} Hypoxemia during intubation is associated with an increased risk of cardiac arrest and death.^{3,4} Identifying interventions to prevent hypoxemia during emergency tracheal intubation is a high priority for clinicians and researchers.^{5,6} Because patients are typically apneic between induction of anesthesia and intubation but continue to consume oxygen, the oxygen content in the lungs at the time of induction is a primary determinant of whether the patient will experience hypoxemia. Preoxygenation, the administration of supplemental oxygen prior to induction of anesthesia, increases the oxygen content in the lung at induction and decreases the risk of hypoxemia.^{7,8} In current clinical practice, preoxygenation for emergency tracheal intubation of critically ill adults is most commonly administered using either an oxygen mask or noninvasive ventilation.¹

Preoxygenation with an oxygen mask is typically performed using either a non-rebreather mask or a bag-mask device. A non-rebreather mask is a loose-fitting mask with an oxygen reservoir connected to an oxygen source. A bag-mask device is a mask capable of forming a tight seal over the mouth when held in place by a clinician and can be used to provide supplemental oxygenation alone, or both supplemental oxygen and manual ventilation.⁹ Both types of oxygen mask can deliver up to 100% oxygen, are simple to set up, and have low potential for gastric insufflation. However, oxygen masks may deliver oxygen less effectively in critically ill patients when tachypnea, high minute ventilation, and poor mask seal allow the entrainment of ambient air with resulting alveolar oxygen concentrations as low as 50%.^{7,10}

Preoxygenation is also routinely administered via noninvasive ventilation, in which a tight-fitting mask is connected to a machine capable of providing both 100% oxygen and positive pressure ventilation. Compared to an oxygen mask, noninvasive ventilation may reduce air entrainment by delivering a higher inspiratory flow rate of oxygen and by minimizing leaks. Additionally, noninvasive ventilation increases the mean airway pressure and recruits atelectatic lung, potentially reducing shunting. Compared with an oxygen mask, noninvasive ventilation may take longer to initiate and may potentially increase the risk of gastric insufflation and aspiration.

Two small, randomized trials have compared these two approaches to preoxygenation. The first trial found that, among 53 ICU patients undergoing tracheal intubation in two hospitals in France, noninvasive ventilation increased the lowest oxygen saturation compared to an oxygen mask (mean lowest oxygen saturation 93% vs. 81%, respectively, $P<0.001$) with no difference between groups in the incidence of aspiration (6% vs. 8%).¹¹ Among 201 ICU patients in 6 hospitals in France, the second trial found no difference in the severity of illness in the 7 days after intubation and an incidence of hypoxemia during intubation of 18.4% in the noninvasive ventilation group versus 27.7% in the oxygen mask group ($P = 0.10$).¹² Thus, whether noninvasive ventilation for preoxygenation in critically ill adults undergoing emergency tracheal intubation decreases the incidence of hypoxemia compared to an oxygen mask remains unknown. Therefore, we designed the PRagmatic trial Examining OXygenation prior to Intubation (PREOXI) to test the hypothesis that, among critically ill adults undergoing emergency tracheal intubation in the ED and ICU, preoxygenation with noninvasive

ventilation will decrease the incidence of hypoxemia compared to preoxygenation with an oxygen mask.

METHODS AND ANALYSIS

This manuscript was written in accordance with Standard Protocol Items: Recommendations for Interventional Trials (SPIRIT) guidelines (see Table 1 and online supplement file 1, section 1).¹³

Funding:

Funding for this trial was provided by the Department of Defense, Defense Health Agency, J9 Office, RESTORAL program. The funder has no role in study design or conduct, data collection or analysis.

Patient and public involvement:

Materials used to communicate about the study with patients and families were developed with input from the Vanderbilt Community Engaged Research Core, which includes input from patients and community members. Study authors will disseminate the results of this study online and via social media in forms suitable for public understanding.

Study Design:

PREOXI is a pragmatic, multicenter, non-blinded, parallel-group, randomized trial comparing preoxygenation with noninvasive ventilation to preoxygenation with an oxygen mask among critically ill adults undergoing emergency tracheal intubation in the ED and ICU. The primary outcome is the incidence of hypoxemia, defined as a peripheral oxygen saturation < 85% between induction of anesthesia and two minutes after intubation. The trial is conducted by the Pragmatic Critical Care Research Group (www.pragmaticcriticalcare.org). An independent data and safety monitoring board (DSMB) is monitoring the progress and safety of the trial. The trial was registered prior to initiation of enrollment (ClinicalTrials.gov identifier: NCT05267652).

Study Population:

Patients located in a participating ED or ICU who are undergoing tracheal intubation using a laryngoscope and sedation are eligible. Patients are excluded if they are known to be less than 18 years old, are known to be pregnant or a prisoner, require positive pressure ventilation for apnea or hypopnea, or have an immediate need for tracheal intubation that precludes performance of study procedures, or if the clinician performing the procedure (referred to as the “operator”) determines that preoxygenation with noninvasive ventilation or an oxygen mask is either required or contraindicated.

Complete lists of inclusion and exclusion criteria are provided in Table 2.

Randomization and treatment allocation:

Patients are randomized in a 1:1 ratio to undergo preoxygenation with noninvasive ventilation vs oxygen mask in permuted blocks of variable size, stratified by

study site. Study-group assignments are generated using a computerized randomization sequence, placed in sequentially numbered opaque envelopes, and distributed to enrolling sites. Before opening the envelope, the operator determines that the patient meets eligibility criteria. Study group assignment remains concealed to study personnel and treating clinicians until after the decision has been made to enroll the patient and the envelope is opened. Patients are considered to be enrolled once the operator opens the opaque trial envelope to reveal study group assignment. After randomization, patients, treating clinicians, and study personnel are not blinded to study group assignment due to the nature of the study intervention.

STUDY INTERVENTIONS

Training:

Before beginning enrollment at each site, study investigators provide training on study procedures including instructional videos with consensus best practice recommendations for preoxygenation with noninvasive ventilation and preoxygenation with an oxygen mask. Observers receive in-person training on the collection of data during the intubation procedure using example data collection sheets. Descriptions of the training videos and website links can be found in the supplementary appendix.

Noninvasive ventilation group:

For patients assigned to the noninvasive ventilation group, operators are instructed to administer noninvasive ventilation via a tight-fitting mask covering the nose and mouth connected to either a conventional mechanical ventilator or a dedicated

noninvasive ventilator (i.e., BiPAP machine) from the initiation of preoxygenation until the initiation of laryngoscopy. The trial protocol does not dictate brand or type of ventilator, ventilator settings, or duration of preoxygenation. Operators receive the following best practice recommendations for the administration of preoxygenation using noninvasive ventilation:

1. Preoxygenate \geq 3 minutes (if feasible)
2. Continue noninvasive ventilation until initiation of laryngoscopy
3. Fraction of Inspired Oxygen (FiO₂) of 100%
4. Expiratory pressure \geq 5 cm of water
5. Inspiratory pressure \geq 10 cm of water
6. Respiratory rate of \geq 10

Oxygen mask group:

For patients assigned to the oxygen mask group, clinicians are instructed to administer supplemental oxygen via a non-rebreather mask or bag-mask device without manual ventilation from the initiation of preoxygenation until the induction of anesthesia. The operator determines whether to use a non-rebreather mask or a bag-mask device without manual ventilation. The trial protocol does not dictate the brand or type of non-rebreather or bag-mask device or duration of preoxygenation. Between induction of anesthesia and initiation of laryngoscopy, the operator determines whether to provide oxygen with a non-rebreather mask, oxygen with a bag-mask device without manual ventilation, or oxygen with a bag-mask device with manual ventilation.² Operators

receive the following best practice recommendations for the administration of preoxygenation using an oxygen mask:

1. Preoxygenate \geq 3 minutes (if feasible)
2. Maximal oxygen flow rate possible (\geq 15 liters per minute)
3. Continue oxygenation from induction to laryngoscopy

Cointerventions:

Study group assignment determines only the initial method of preoxygenation.

Treating clinicians determine all other aspects of the intubation procedure including: [1] the co-administration of supplemental oxygen by nasal cannula (either standard nasal cannula, large bore nasal cannula, or heated high flow nasal cannula) before induction, between induction and initiation of laryngoscopy, and between initiation of laryngoscopy and intubation of the trachea; [2] choice of induction medication and timing of administration; [3] use of neuromuscular blockade; [4] choice of laryngoscope; [5] use of additional airway management equipment and adjuncts; and [6] post-intubation ventilator settings.

Data Collection

An observer not directly involved with the intubation procedure collects data for key periprocedural outcomes, including oxygen saturation at induction and the lowest value for oxygen saturation between induction and two minutes after successful intubation. Observers may be clinical personnel on the enrolling unit (e.g., physicians or nurses) or research personnel. Immediately after the intubation procedure, the operator

completes a paper data collection form to record the device used for preoxygenation, the duration of preoxygenation, the devices used for oxygenation and ventilation between induction and laryngoscopy, and complications of intubation.¹⁴ Study personnel at each site review the medical record to collect data on baseline characteristics, pre- and post-laryngoscopy management, and clinical outcomes. A complete list of baseline, peri-procedural, and in-hospital variables are provided in Supplemental Table 1.

Data on pneumothorax and new pulmonary infiltrates are collected by study staff from clinical radiology reports using a structured case report form. The clinical radiologist who interprets the chest imaging is unaware of study group assignment. A lung infiltrate is considered to be present if the clinical radiologist identifies on the chest imaging the presence of air bronchograms, centrilobular nodules, consolidation, ground-glass opacity, infiltrate, opacity, parenchymal opacification, pneumonia, pneumonitis, pulmonary edema, or a tree-in-bud pattern. A pneumothorax or lung infiltrate present on chest imaging in the 24 hours after intubation will be assumed to be new if it was not present on chest imaging in the 24 hours prior to intubation. If no chest imaging is available in the 24 hours prior to intubation, any pneumothorax or lung infiltrate on chest imaging will be assumed to be new.

Primary Outcome

The primary outcome is the incidence of hypoxemia, defined as a peripheral oxygen saturation <85% during the interval between induction and 2 minutes after intubation.

We selected hypoxemia (as a binary variable) rather than lowest oxygen saturation (a continuous variable) as the primary outcome for the trial for several reasons. First, experiencing hypoxemia in the range associated with an increased risk of adverse clinical outcomes (e.g., cardiac arrest) may be more clinically relevant than changes in oxygen saturation within the normal range. For example a change in oxygen saturation of 5 percentage points from 87% to 82% may be more closely associated with adverse outcomes than a change in oxygen saturation of 10 percentage points from 100% to 90%. Second, values for oxygen saturation are “right-censored” because oxygen saturation reaches 100% with a partial pressure of oxygen in arterial blood (PaO_2) of approximately 100 mmHg but patients may have a higher PaO_2 following preoxygenation. The approach of analyzing hypoxemia as a binary variable rather than lowest oxygen saturation has been used by many prior trials and endorsed by airway experts.¹⁵⁻²⁰

We selected an oxygen saturation of <85% as the threshold for the primary outcome based on several physiologic and procedural factors. First, an oxygen saturation of 85% corresponds with the inflection point on the oxyhemoglobin dissociation curve, at which further decrements in arterial oxygen concentrations result in rapid and critical desaturation.⁹ Second, an oxygen saturation <85% has been associated with an increased risk of cardiac arrest during tracheal intubation²¹ and may be associated with increased mortality.⁵

Secondary Outcome:

The sole secondary outcome is the lowest oxygen saturation during the interval between induction and 2 minutes after tracheal intubation.

Additional Outcomes:

Table 3 reports the safety outcomes, exploratory outcomes, and clinical outcomes.

Sample Size Estimation

The minimum clinically important difference in the incidence of hypoxemia that would be required to justify routine preoxygenation with noninvasive ventilation rather than preoxygenation with an oxygen mask during the emergency tracheal intubation of critically ill adults is uncertain. The current trial is designed to detect a 6% absolute difference between groups in the incidence of hypoxemia, a difference that is similar to or smaller than the difference considered to be clinically meaningful in the design of prior trials of oxygenation strategies during tracheal intubation.^{2,24} Assuming an incidence of hypoxemia of 17% in the oxygen mask group based on data from two recently completed trials by this network in similar ED and ICU settings, detecting a 6% absolute decrease in the incidence of hypoxemia with 85% power at a two-sided alpha level of 0.05 would require enrollment of 1,264 patients (632 per group).^{25,26} Anticipating missing data for up to 3% of patients, we will plan to enroll a maximum of 1,300 total

patients (650 per group). This sample size calculation was performed in PS version 3.1.2 (Nashville, Tennessee).

Data and Safety Monitoring Board and Interim Analysis

A data and safety monitoring board (DSMB) consisting of members with expertise in bioethics, emergency medicine, pulmonary and critical care medicine, anesthesiology, biostatistics, and clinical trial methodology has overseen the design of the trial and is monitoring its conduct. The DSMB will review a single interim analysis, prepared by the study biostatistician at the anticipated halfway point of the trial after enrolment of 650 patients. The pre-specified stopping boundary for efficacy is a P value < 0.001 using a Chi-square test for the difference between groups in the primary outcome. This conservative Haybittle–Peto boundary will allow the final analysis to be performed using an unchanged level of significance (two-sided P value < 0.05).

The DSMB has the authority to recommend that the trial stop at any point, request additional data, request additional interim analyses, or request modifications to the study protocol.

Statistical Analysis Principles

Analyses will be conducted following reproducible research principles using R (R Foundation for Statistical Computing, Vienna, Austria). Categorical variables will be presented as number and percentage and compared between groups using a Chi-square test. Continuous variables will be presented as mean \pm SD or median and IQR and compared between groups using a Wilcoxon Rank Sum test. We will also present

absolute between-group differences with associated 95% confidence intervals. A two-sided P-value of < 0.05 will define a statistically significant between-group difference in the primary outcome. With a single primary outcome, no adjustment for multiplicity will be made. For secondary, safety, and exploratory analyses, emphasis will be placed on the magnitude of differences between groups with 95% confidence intervals rather than statistical significance.

Main Analysis of the Primary Outcome

The main analysis will be an unadjusted, intention-to-treat comparison of the primary outcome of hypoxemia between patients randomized to the noninvasive ventilation group versus patients randomized to the oxygen mask group, using a chi-square test. The absolute difference in proportions, associated 95% confidence interval, and a P value for the comparison will be presented. The primary analysis will be conducted among patients for whom the primary outcome is available without imputation of missing data.

Additional Analyses of the Primary Outcome

Multivariable analysis

